13.0 Potential Benefits to Subjects or Others

This study is for research purposes only. There is no direct benefit to you from your participation in the study. Information learned from the study may help other people in the future.

14.0 Sharing of Results with Subjects

Information about the subjects (including your identifiable private information) may have all of their identifiers removed and used for future research studies.

Records of the subjects' participation in this study will be held confidential except as disclosure is required by law or as described in the ICF.

15.0 Payment

For participating in this study, participants will be compensated \$50 per visit for a maximum of \$150. This payment will be mailed to each participant within four weeks after completion of each visit.

18.0 Devices

Dispensing and storage of SinuSonic devices will be done by the study team. All SinuSonic devices will be stored on the 11th floor of Rutledge Tower in Room 1126 and locked in a cabinet for ambient storage. The device will be dispensed in the Outpatient Sinus Clinic. Only study participants will receive the SinuSonic for use.

19.0 DATA SAFETY MONITORING AND REPORTING

Safety data listings will be reviewed by Principal Investigator, Co-Investigators, and the research team at regular intervals throughout the study.

Safety will be monitored throughout the study based on monitoring of adverse events, performing nasal exams, measuring vital signs (ie blood pressure, pulse) and weight, and through collection of concomitant medication information.

The period of observation for collection of non-serious adverse events extends from the time the subject gives informed consent until completion of the End-of-study visit or Early Termination Visit. Serious adverse events (SAE) will be reported to the MUSC IRB and to the sponsor from the time of informed consent through 30 days after the last use of the SinuSonic. Adverse event data listings will be reviewed by the principal investigator, co-investigators, and the research team at regular intervals throughout the study.

All AEs, regardless of seriousness or relationship to SinuSonic use, spanning from the signature of the informed consent form until the end of the study as defined by the protocol for that patient, are to be reported to the Healthy Humming, LLC. All AEs which follow the MUSC IRB qualifications will also be reported to the MUSC IRB within 24 hours of site knowledge of the event.

The Investigator will take appropriate measures to follow all AEs until clinical recovery is complete and laboratory results have returned to normal, or until progression has been stabilized, or until death, in order to ensure the safety of the patients. This may imply that observations will continue beyond the last planned visit per protocol, and that additional investigations may be requested by the monitoring team up to as noticed by Healthy Humming, LLC.

In the case of occurrence of an SAE, the Investigator will immediately (within 24 hours) report the event to Healthy Humming, LLC and to the MUSC IRB, as applicable.

References

Appendix

Attachment 1: Patient Medical History

SinuSonic Study

PI: [name]

Subject ID#:

Subjects Initials:

OVER THE LAST 2 WEEKS, HOW TROUBLESOME HAS THE FOLLOWING SYMPTOM BEEN?
PLEASE PLACE A MARK ON THE LINE.

	Not troublesome thinkable/troublesome	Worst
Nasal blockage/obstruction/congestion		

DEMOGRAPHIC AND CLINICAL VARIABLES (If not previously collected):

Age at enrollment (years):

--	--

Gender: Male Female

What is/was your profession (current/retired)? _____

LANGUAGE, ETHNICITY, RACE, MARITAL STATUS

Please mark one of the following categories which describes your native language:

- American English
- Other: please specify _____

Please mark one of the following categories which describes your ethnicity:

- Not Hispanic or Latino
- Hispanic or Latino

Please mark one or more of the following categories which describes your race:

- American Indian or Alaska Native
- Asian
- Black or African American
- Native Hawaiian or Other Pacific Islander
- White
- Other

SMOKING HISTORY

1. Do you currently smoke tobacco products? Yes No (If No please go to question 2)

How many tobacco products do you use in a day? _____ Singles Packs

2. Are you currently exposed to secondhand smoke? Yes No (If No please skip ahead)

How many years have you been exposed to secondhand smoke? _____

How many hours a day are you exposed to secondhand smoke? _____

CURRENT MEDICATION USAGE

 Nasal steroid sprays (Flonase, Nasonex, etc)	 Yes	 No
 Nasal antihistamine spray (Astelin, etc)	 Yes	 No
 Oral antihistamines (Allegra, Claritin, Benedryl, etc)	 Yes	 No
 Oral decongestant (Sudafed, etc)	 Yes	 No
 Mucolytic (Mucinex, etc)	 Yes	 No
 Luekotriene (Singulair, etc)	 Yes	 No

COMORBID MEDICAL CONDITIONS: Check box and provide details if present

 Depression history:	 Resolved/past diagnosis	 Present/medicated	 Present/not medicated
 Anxiety history:	 Resolved/past diagnosis	 Present/medicated	 Present/not medicated
 Obstructive Sleep Apnea:	 Currently being treated	 History / No current treatment	
 Allergic rhinitis:	_____		
 Previous allergy testing (blood test or skin prick):	 Yes	 No	
 Immunotherapy shots for allergies:	 Yes	 No	 Currently
 Asthma	 Yes	 No	

 Height (ft/in):	_____
 Weight (lbs):	_____

Attachment 2: Baseline Questionnaires**BASELINE QUESTIONNAIRES**

PATIENT QUESTIONS													
How long have you had nasal problems?	<3 months 3-6 months 6-12 months 1-3 years >3 years												
OVER THE LAST WEEK, HOW TROUBLESONE HAVE THE FOLLOWING SYMPTOMS BEEN? PLEASE PLACE A MARK ON THE LINE.													
	
  
 Not troublesome	Worst thinkable/troublesome	
   
 ◆————◆	◆————◆	
  
	Not troublesome	Worst thinkable/troublesome	◆————◆	◆————◆	◆————◆	◆————◆	◆————◆	◆————◆	◆————◆	◆————◆	◆————◆	◆————◆
Not troublesome	Worst thinkable/troublesome												
◆————◆	◆————◆												
◆————◆	◆————◆												
◆————◆	◆————◆												
◆————◆	◆————◆												
◆————◆	◆————◆												
Nasal blockage/obstruction/congestion	◆————◆												
Nasal discharge/drainage out of the front or back of nose	◆————◆												
Pain/pressure in nose or sinuses	◆————◆												
Sense of smell	◆————◆												
OVERALL ASSESSMENT OF NASAL AND SINUS PROBLEMS	◆————◆												

BASELINE Total Nasal Symptom Score

Please answer all questions to the best of your ability. This information will assist us in understanding and treating symptoms. Please rate how your symptoms have been over the **past week**.

Symptom	None	Mild: Symptom clearly present but easily tolerated	Moderate: Symptom bothersome but tolerable	Severe: Symptom difficult to tolerate – interferes with activities
Nasal congestion/obstruction	0	1	2	3
Runny nose/secretions	0	1	2	3
Nasal itching	0	1	2	3
Sneezing	0	1	2	3
Sleep difficulty with nasal symptoms	0	1	2	3

BASELINE NOSE scale

Please help us to better understand the impact of nasal obstruction on your quality of life by completing the following survey. Thank you!

Over the past **ONE month**, how much of a problem were the following conditions for you?

	Not a problem	Very mild problem	Moderate problem	Fairly bad problem	Severe problem
Nasal congestion or stuffiness	0	1	2	3	4
Nasal blockage or obstruction	0	1	2	3	4
Trouble breathing through my nose	0	1	2	3	4
Trouble sleeping	0	1	2	3	4
Unable to get enough air through my nose during exercise or exertion	0	1	2	3	4

Attachment 3: Baseline SNOT-22

BASELINE SNOT22

Problem as bad as it can be	Severe Problem	Moderate Problem	Mild or slight problem	Very mild problem	No problem	
0	1	2	3	4	5	1. Considering how severe the problem is when you experience it and how frequently it happens, please rate each item below on how "bad" it is over the last 2 weeks by circling the number that corresponds with how you feel using this scale: →
0	1	2	3	4	5	1. Need to blow nose
0	1	2	3	4	5	2. Sneezing
0	1	2	3	4	5	3. Runny nose
0	1	2	3	4	5	4. Cough
0	1	2	3	4	5	5. Post-nasal discharge
0	1	2	3	4	5	6. Thick nasal discharge
0	1	2	3	4	5	7. Ear fullness
0	1	2	3	4	5	8. Dizziness
0	1	2	3	4	5	9. Ear pain
0	1	2	3	4	5	10. Facial pain/pressure
0	1	2	3	4	5	11. Difficulty falling asleep
0	1	2	3	4	5	12. Wake up at night
0	1	2	3	4	5	13. Lack of a good night's sleep
0	1	2	3	4	5	14. Wake up tired
0	1	2	3	4	5	15. Fatigue
0	1	2	3	4	5	16. Reduced productivity
0	1	2	3	4	5	17. Reduced concentration
0	1	2	3	4	5	18. Frustrated/restless/irritable
0	1	2	3	4	5	19. Sad

20. Embarrassed	0	1	2	3	4	5
21. Loss of smell or taste	0	1	2	3	4	5
22. Nasal obstruction	0	1	2	3	4	5

Attachment 4: Follow Up Questionnaire**FOLLOW UP 5 MINUTES**

AFTER USING SINUSONIC, HOW TROUBLESOME ARE THE FOLLOWING SYMPTOMS? PLEASE PLACE A MARK ON THE LINE.		
	Not troublesome	Worst thinkable/troublesome
Nasal blockage/obstruction/congestion		
Nasal discharge/drainage out of the front or back of nose		
Pain/pressure in nose or sinuses		
Sense of smell		
OVERALL ASSESSMENT OF NASAL AND SINUS PROBLEMS		

[figure not shown]
[figure not shown]
Change in nasal symptoms and use of device

Please rate changes in your nasal symptoms and use of device.

Symptom	None	Mild	Moderate	High
Improvement in nasal obstruction/stuffiness	0	1	2	3
Improvement in nasal drainage/discharge	0	1	2	3
Improvement in nasal or sinus pressure	0	1	2	3
Improvement in ability to smell	0	1	2	3
Pain with use of device	None	Mild	Moderate	Severe
Comfort and ease of use	Poor	Low	Moderate	High
Bleeding:	Yes	No		

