9.1 Schedule of Events

Phase	Screening	Treatment		
		0	2	4-6
Week	0	0	2	4-6
Visit	1	2	3	4
Informed Consent	x			
Inclusion/Exclusion Criteria	x			
Medical History	x			
Height	x			
Rhinoscopy	x		x	
Vital Signs	x			
Pregnancy Test	x			
Distribution of SinuSonic	x			
NOSE Questionnaire	x		x	x
SNOT-22	x		x	x
TNSS Questionnaire	x		x	x
Global Assessment of Nasal/Sinus Problems	x	x	x	x
PNIF	x	x	x	

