10.0 Data Management

All analyses and graphs will be performed with SPSS 24.0, Sample Power 3.0, and Sigma Plot 10.0 (SPSS, Chicago, IL.). Disease information and demographic variables, such as age, gender, race, quality of life (QOL) scores, and VAS scores will be summarized using frequencies, means, and standard deviation as appropriate. Outcome metrics will be compared between baseline and 5 minutes (AIM 1), baseline and 2 weeks (AIM 2), and baseline and 4-6 weeks (AIM 3). Categorical variables will be compared using Chi Square or McNemar's test. Continuous variables will be compared using One-Way ANOVA with repeated measures followed by post-hoc analysis. Data regarding safety and patient satisfaction will be summarized for each time point. A p-value ≤ 0.05 will be considered statistically significant. Due to the exploratory nature of this study, no p-value correction (ie Bonferroni) will be applied. If appropriate, subgroup analysis can be performed based on underlying disease classification (allergic rhinitis, nonallergic rhinitis, CRSsNP, CRSwNP).

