Attachment 5: 2-Week Follow Up

FOLLOW UP 2 WEEKS
PHYSICIAN ASSESSMENT

OVER THE LAST WEEK, HOW TROUBLESOME HAVE THE FOLLOWING SYMPTOMS BEEN? PLEASE PLACE A MARK ON THE LINE.	
	Not troublesome Worst thinkable/troublesome
Nasal blockage/obstruction/congestion	
Nasal discharge/drainage out of the front or back of nose	
Pain/pressure in nose or sinuses	
Sense of smell	
OVERALL ASSESSMENT OF NASAL AND SINUS PROBLEMS	

Change in nasal symptoms and use of device

Please rate changes in your nasal symptoms and use of device.

Symptom	None	Mild	Moderate	High
Improvement in nasal obstruction/stuffiness	0	1	2	3
Improvement in nasal drainage/discharge	0	1	2	3
Improvement in nasal or sinus pressure	0	1	2	3
Improvement in ability to smell	0	1	2	3
Use of the Device				
Pain with use of device	None	Mild	Moderate	Severe
Comfort and ease of use	Poor	Low	Moderate	High
Bleeding:	Yes	No		
Willingness to use again	Yes	No		
Willingness to recommend to friend/family	Yes	No		

Total Nasal Symptom Score

Please answer all questions to the best of your ability. This information will assist us in understanding and treating symptoms. Please rate how your symptoms have been over the **past week**.

Symptom	None	Mild: Symptom clearly present but easily tolerated	Moderate: Symptom bothersome but tolerable	Severe: Symptom difficult to tolerate – interferes with activities
Nasal congestion/obstruction	0	1	2	3
Runny nose/secretions	0	1	2	3
Nasal itching	0	1	2	3
Sneezing	0	1	2	3
Sleep difficulty with nasal symptoms	0	1	2	3

NOSE Scale

Please help us to better understand the impact of nasal obstruction on your quality of life by completing the following survey. Thank you!

Over the past **ONE month**, how much of a problem were the following conditions for you?

	Not a problem	Very mild problem	Moderate problem	Fairly bad problem	Severe problem
Nasal congestion or stuffiness	0	1	2	3	4
Nasal blockage or obstruction	0	1	2	3	4
Trouble breathing through my nose	0	1	2	3	4
Trouble sleeping	0	1	2	3	4
Unable to get enough air through my nose during exercise or exertion	0	1	2	3	4

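### The single-use (AIM 1) VAS comparison sets a past-week rating against an after-use rating, and no current-state VAS is taken before use

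*Combined protocol and SAP*

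**What the plan says.** The primary objective (Section 1.0) is the safety and efficacy of a single use of the device. Section 10.0 sets out the comparisons: "Outcome metrics will be compared between baseline and 5 minutes (AIM 1), baseline and 2 weeks (AIM 2), and baseline and 4-6 weeks (AIM 3"). Continuous variables go into a one-way repeated-measures ANOVA with post-hoc analysis.

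The VAS forms are worded as follows:

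- **Before use, five lines (Attachment 2):** "OVER THE LAST WEEK, HOW TROUBLESONE HAVE THE FOLLOWING SYMPTOMS BEEN".
- **Before use, congestion line only (Attachment 1):** "OVER THE LAST 2 WEEKS, HOW TROUBLESOME HAS THE FOLLOWING SYMPTOM BEEN".
- **5 minutes, the same five lines (Attachment 4):** "AFTER USING SINUSONIC, HOW TROUBLESOME ARE THE FOLLOWING SYMPTOMS".
- **2 weeks (Attachment 5) and 5 weeks (Attachment 7), the same five lines:** "OVER THE LAST WEEK, HOW TROUBLESOME HAVE THE FOLLOWING SYMPTOMS BEEN".

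The schedule in Section 9.1 marks two outcome rows at Visit 2, the week-0 treatment visit: the "Global Assessment of Nasal/Sinus Problems" row and PNIF. NOSE, SNOT-22 and TNSS are not marked there.

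**The concern.** A before-and-after comparison assumes that the same quantity is rated twice. In AIM 1 it is not. The first rating summarises a week and the second describes the moment after use. A subject whose nose happens to be clearer in clinic than over the past week will appear to improve even if the device does nothing. A subject who is more blocked than usual that day may show no change despite a real benefit.

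With no control arm, nothing cancels this gap. With no current-state rating before use, nothing collected allows it to be estimated afterwards. The comparison serves the primary objective, and Section 2.0 says that effectiveness will be measured through patient responses. The VAS is the only symptom scale scored on both sides of the single use.

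**Working it through.** **1. Comparing the wording.**

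| Form | When completed | Period rated |
|---|---|---|
| Attachment 1 (congestion only) | before use | last 2 weeks |
| Attachment 2 (five lines) | before use | last week |
| Attachment 4 (five lines) | 5 minutes | after use, present tense |
| Attachment 5 (five lines) | 2 weeks | last week |
| Attachment 7 (five lines) | 5 weeks | last week |

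The 2-week and 5-week forms match the Attachment 2 baseline, so AIMs 2 and 3 are like-for-like on this point. Only AIM 1 is mismatched. The Visit 2 mark for the global assessment does not supply a pre-use rating, because the only form provided for that time is the post-use one.

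**2. What the AIM 1 difference contains.** Let W be the past-week rating, S0 the unrecorded state just before use and S5 the rating at 5 minutes. Then

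W − S5 = (W − S0) + (S0 − S5).

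The second bracket is the change of interest. The first is the recall gap. S0 is never collected, so the two cannot be separated.

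**3. Illustration of size.** The plan gives no power, effect size or SD, so there is no figure of its own to reproduce. The inputs are:

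- n = 40 (Section 5.0) and a threshold of 0.05 (Section 10.0).
- Assumed: a two-sided test, a paired-difference SD of 2.0 to 3.0 points on the 10-point VAS, and mean gaps of 0 to 1.0 point.
- The test is a paired t-test, which equals a repeated-measures ANOVA with two time points (F = t²).

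The rejection rate comes from the noncentral t distribution with 39 degrees of freedom and noncentrality gap × √40 / SD. For a gap of 0.5 and SD 2.0, this is 0.5 × 6.325 / 2.0 = 1.58. With a critical value of 2.023, the rejection rate is 0.338.

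Chance of p ≤ 0.05 with no true change:

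| Mean gap | SD 2.0 | SD 2.5 | SD 3.0 |
|---|---|---|---|
| 0 | 0.050 | 0.050 | 0.050 |
| 0.25 | 0.120 | 0.095 | 0.081 |
| 0.5 | 0.338 | 0.235 | 0.177 |
| 1.0 | 0.869 | 0.694 | 0.538 |

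The rates are the same for a gap of opposite sign. A smaller SD raises them: at SD 1.5, gaps of 0.5 and 1.0 give 0.538 and 0.984. The smallest mean change that reaches significance is 2.023 × SD / √40, which is 0.64, 0.80 and 0.96 points for SD 2.0, 2.5 and 3.0.

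**4. The masking case.** Suppose a true improvement of 1.0 point and a gap of 0.5 against it. The net change is 1.0 − 0.5 = 0.5, which is detected in 0.338, 0.235 and 0.177 of trials. Without the gap the figures are 0.869, 0.694 and 0.538.

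**The case against.** - **Scope.** This is a 40-subject exploratory pilot, and the mismatch touches one instrument at one time point. PNIF, marked at Visits 1 and 2, has no recall period and gives a like-for-like AIM 1 measure. This is correct and limits the severity. However, PNIF measures airflow and does not stand in for the discharge, pain/pressure and smell lines.
- **Role of the VAS.** Section 10.0 compares unnamed outcome metrics and mentions VAS scores only among variables to be summarised. The schedule has no row called VAS. Treating the five lines as an AIM 1 outcome is therefore an inference. It is a reasonable one, because the same five lines are on both the baseline and 5-minute forms.
- **Change ratings.** The 5-minute form also asks for direct ratings such as "Improvement in nasal obstruction/stuffiness". These need no baseline score, so the mismatch does not enter them. The form does not say what they are compared with, however, and a subject could have the past week in mind. That gives no reassurance about the VAS.
- **Magnitude.** Gap, SD and true effect are all assumed, and the rates follow from those choices. Section 10.0 also does not say which time points enter the ANOVA, so the paired test is a stand-in. Both points are fair. The finding rests on the wording of the forms, not on these rates.
- **Other biases.** Entry requires a congestion VAS above 5 and there is no control arm, so regression to the mean and expectation can produce a fall even with matched wording. This is true, but those problems need a control arm, whereas this one needs a form.

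**Conclusion.** The concern holds. As the forms are written, the AIM 1 VAS change mixes any change after use with a change in the period being rated, and no collected item separates them. Confidence is high for the mismatch itself. Its size and direction cannot be known from the documents.

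Under the stated assumptions, the wording alone would raise the chance of a significant result from 5% to 8–12% for a quarter-point gap, 18–34% for half a point and 54–87% for one point. An opposing gap could mask a real effect. The 5% reference allows for no other pre-post bias.

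PNIF, the pain, comfort and bleeding items, and the VAS in AIMs 2 and 3 are unaffected. This should be fixed: it bears on the primary objective and is cheap to correct, but it is confined to the VAS part of AIM 1.

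**What to change.** 1. Immediately before the 3-minute in-clinic use, collect the same five VAS lines with a present-moment stem, for example: *Right now, how troublesome are the following symptoms?*
2. Use the identical stem on the 5-minute form. That form is already in the present tense, so this is for exact matching. The added pre-use form is the essential step.
3. Add a row for it to Section 9.1. State in Section 10.0 that this rating is the AIM 1 VAS baseline, analysed as its own paired contrast with 5 minutes.
4. Keep the past-week VAS as the baseline for AIMs 2 and 3, with its repeated-measures ANOVA using baseline, 2 weeks and 4–6 weeks.

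The cost is a half-page form, a wording change, one schedule row, one sentence and about a minute of each subject's time. The 5-minute VAS would no longer share a baseline with the later VAS in a single ANOVA, but Section 10.0 already lists the three aims as separate comparisons. Marking identical lines minutes apart may also encourage anchoring or expected-improvement answers. The change removes only the recall mismatch.

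If data are already collected, report all AIM 1 measures, rely mainly on PNIF for the before-and-after comparison, and present the VAS change with this limitation stated.

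### Comfort and ease of use share one rating, with unclearly ordered low anchors, on all three follow-up forms, so answers below High cannot be attributed to either property (minor)

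*Combined protocol and SAP*

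**What the plan says.** Attachment 4 (5 minutes), Attachment 5 (2 weeks) and Attachment 7 (5 weeks) all carry the row "Comfort and ease of use". Each takes a single answer from Poor, Low, Moderate and High. On all three forms the row directly above is "Pain with use of device", answered None, Mild, Moderate or Severe, and the row below records bleeding as yes or no.

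The 2-week and 5-week forms also ask "Willingness to use again" and "Willingness to recommend to friend/family", each as yes or no. The 5-minute form asks neither.

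Section 10.0 states the use to be made of these answers: "Data regarding safety and patient satisfaction will be summarized for each time point". It does not list the items that make up satisfaction, rank them, or combine them into a score.

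**The concern.** The row asks two questions and accepts one answer. A subject who finds the device comfortable but awkward, or easy but unpleasant, has no correct box and must either ignore one half or average the two.

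The anchors add to the difficulty. Poor is a word of quality, while Low, Moderate and High are words of amount, so it is not evident that Poor is the step below Low.

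What is at stake is the descriptive summary of satisfaction and tolerability. In a pilot of a device, discomfort and handling difficulty call for different responses: one points to the device, the other to the instructions. A combined answer does not show which is needed.

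**Working it through.** The plan gives no figure to reproduce for this item. The check sets the sections side by side and then bounds the possible effect.

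**1. Are the two properties separable for this device?** Section 3.1 treats them as different things. Handling includes the 45-degree hold, the trial blow into the mask, and finding the flutter sound and finding it again after nose-blowing. Sensation includes resistance on breathing out and vibration. The same section allows for subjects who cannot breathe in through the nose, so difficulty without discomfort is foreseeable.

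**2. Does another row separate them?** In part. Pain and bleeding have their own rows on every form, so a low combined rating can be read against the same subject's pain answer. What stays mixed is non-painful discomfort (mask, resistance, vibration) and handling difficulty.

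**3. Which satisfaction-type items does each form carry?** Section 10.0 gives no list, so this classification is an assumption.

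| Form | Combined row | Use again | Recommend | Total |
|---|---|---|---|---|
| 5 minutes (Att. 4) | yes | no | no | 1 |
| 2 weeks (Att. 5) | yes | yes | yes | 3 |
| 5 weeks (Att. 7) | yes | yes | yes | 3 |

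The combined row stands alone only at 5 minutes. Sections 1.0 and 10.0 make that the time point of the primary objective, a single use.

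**4. Which answers are ambiguous?** High plausibly endorses both halves. The ambiguity lies in Poor, Low and Moderate.

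**5. Illustrative bound.** Section 5.0 gives n = 40. The discordant share (10% to 25%), the cut at Moderate or High and the observed rate of 28/40 are assumptions, not figures from the documents.

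- Discordant subjects: 0.10 × 40 = 4, up to 0.25 × 40 = 10.
- Let *a* subjects clear the cut on comfort only and *b* on ease only. If all subjects answered for comfort rather than all for ease, the rate would differ by |a − b|/40.
- With 4 discordant subjects this lies between 0 (a = b = 2) and 4/40 = 10 points. With 10 it lies between 0 (a = b = 5) and 10/40 = 25 points.
- For comparison, the sampling half-width at 28/40 = 70% is 1.96 × √(0.7 × 0.3/40) = 14.2 points. The Wilson 95% interval is 54.6% to 81.9%.
- The upper bound reaches 14.2 points only when at least 0.142 × 40 = 5.7, that is 6, subjects are discordant, all straddle the cut, and all lean the same way. At 4 discordant subjects it stays below sampling error.

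**The case against.** The case against giving this weight is good, and much of it stands. The item is secondary and descriptive, no decision rule uses it, and a labelled answer can be read as a combined impression of usability. A reader might nevertheless draw stronger conclusions that the documents do not support.

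- **That this is the main satisfaction rating at every time point.** Section 10.0 gives no item that status, and the two willingness items at 2 and 5 weeks are more direct measures of satisfaction.
- **That the rating cannot be interpreted.** It can be read as an overall impression. What is lost is the attribution of lower answers to one property.
- **That it hides whether the device hurts.** Pain and bleeding are asked separately on each form, adverse events are collected throughout (Sections 9.0, 11.0 and 19.0), and rhinoscopy is repeated at week 2 (Section 9.1).
- **That the anchors mislead because they run opposite to the pain row.** They do run opposite, but every option has a verbal label and no score summing the rows is planned. The comfort row runs the same way as the improvement rows, such as "Improvement in nasal obstruction/stuffiness", so pain is the reversed row in that table. The exact column layout also cannot be confirmed from extracted text.
- **That a planned trend is at risk because ease may rise while comfort falls.** This could happen, but Section 10.0 specifies no change analysis for the item and the baseline forms contain no version of it.

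What survives is narrower: two properties in one answer, unclear order at the low end, and the same wording on three forms.

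**Conclusion.** The point holds as a minor flaw in a descriptive item. On all three follow-up forms, an answer below High cannot be attributed to non-painful discomfort or to handling difficulty, and the lowest two categories lack a clear order. The loss matters most at 5 minutes, where no other satisfaction-type item is asked.

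Its size cannot be derived from the documents. The 10 to 25 points above are an upper bound under an assumed discordant share, an assumed cut and discordance all in one direction; the shift could be zero. The efficacy comparisons are unaffected.

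**What to change.** In Attachments 4, 5 and 7, replace the combined row with two rows, Comfort during use and Ease of use. Give each a clearly ordered set of anchors, for example Very low, Low, Moderate, High. Under Section 10.0, summarise the two rows separately at each time point; that would also be the place to name the items that count as patient satisfaction.

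The cost is one extra row on each of three forms and one extra summary line, with a few seconds of each subject's time. If any subject has already completed the present forms, answers to the combined row should be reported apart from the new rows, because they cannot be divided afterwards.
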